6.2 Time Point Algorithms

6.2.1 Relative Day

Relative Day will be calculated for both efficacy and safety endpoints. For efficacy endpoints, the following relative day calculation will be used:

The date of randomization will be considered relative day 1, and the day before the randomization will be relative day -1. Relative days will be calculated as follows only when the full assessment date is known (i.e., partial dates will have missing relative days for all assessments except for adverse events, concomitant medications, date of response, date of progression, and date of death, see Section 7.3.1 on imputation of partial dates):

For days on or after randomization:

Date of Assessment – Date of Randomization + 1

For days before randomization:

Date of Assessment - Date of Randomization

For days following disease progression:

Date of Assessment - Date of Disease Progression +1

For safety endpoints, the following relative day calculation will be used:

The date of first dose of sorafenib (control arm) or date of first angiogram (treatment arm) will be considered relative day 1, and the day before the first dose of sorafenib or date of first angiogram will be relative day -1. Relative days will be calculated as follows only when the full assessment date is known (i.e., partial dates will have missing relative days for all assessments except for adverse events, concomitant medications, date of response, date of progression, and date of death):

For days on or after first dose of sorafenib or date of first angiogram:

Date of Assessment – Date of first dose of sorafenib or date of first angiogram + 1 For days before first dose of sorafenib or date of first angiogram:

Date of Assessment – Date of first dose of sorafenib or date of first angiogram

For days following disease progression:

⁵ Subjects to complete questionnaire at each study visit; completion not required for telephone follow-up visits

⁶ Pre-treatment evaluation is always done before the first TheraSphere treatment and prior to subsequent treatments as needed

⁷ TheraSphere must be administered within 4 weeks of randomization

⁸ Images taken up to 28 days in advance of randomization can be used for baseline images

⁹ Imaging to be scheduled every 16 weeks from randomization at alternate Q8 week follow up visits

¹⁰ Document liver treatment medications only; medications used for supportive care do not require documentation

¹¹ A maximum of 2 re-treatments with TheraSphere are allowed following hepatic progression for lesions amenable to TheraSphere treatment

Date of Assessment – Date of Disease Progression +1

6.2.2 Windows

For the purpose of statistical analysis, the visit windows will be calculated as shown below.

Table 3 Analysis Windows for Assessments Performed at Four Week Intervals

| Week | Scheduled Study Day | Visit Window for Analysis (Days) |
|-------------------------|---------------------|----------------------------------|
| Screen | -14 – 0 | -14 – 0 |
| Randomize (Baseline) | 0 | 0 |
| Week 2 | 14 | 1 - 21 |
| Week 4 | 28 | 22 – 42 |
| Week 8 | 56 | 43 – 70 |
| Week 12 | 84 | 71 – 98 |
| Week 16 | 112 | 99 – 126 |
| | | |
| End of Study | | Latest assessment available |

Table 4 Analysis Windows for Assessments Performed at Eight Week Intervals

| Week | Scheduled Study Day | Visit Window for Analysis (Days) |
|-------------------------|---------------------|----------------------------------|
| Screen | -14 – 0 | -14 – 0 |
| Randomize (Baseline) | 0 | 0 |
| Week 8 | 56 | 1 – 84 |
| Week 16 | 112 | 85 – 140 |
| Week 24 | 168 | 141 – 196 |
| | | |
| Disease Progression | P0 | P0 |
| FDP Week 8 | P56 | P1 – P84 |
| FDP Week 16 | P112 | P85-P140 |

| ••• | |
|--------------|-----------------------------|
| End of Study | Latest assessment available |

FDP = Following Disease Progression

Pn = Relative days following disease progression

If a patient has more than 1 assessment occurring in the same visit window, the data from the visit closest to the scheduled study day will be used. If 2 visits have the same distance from the scheduled study day, excluding time to event endpoints, the data of the visit after the scheduled study day will be used. For time to event analyses, the event that occurs first will be used.

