6.5.3 Clinical Laboratory Evaluations

Clinical laboratory results will be converted to SI units.

Laboratory data for safety analysis will be summarized as continuous summaries (ie, as absolute values, and change from baseline to each scheduled visit and end of study treatment in absolute values). Scheduled visits for hematology and coagulation

25

assessments will include Screening, Week 4, Week 8, Week 12, Week 16, Week 20, and Week 24, while scheduled visits for chemistry will include Screening, Week 2, Week 4, Week 8, Week 12, Week 16, Week 20, and Week 24. End of study treatment will be defined as from last dose of TheraSphere or sorafenib to 30 days after treatment.

Laboratory values will also be classified as normal (if value is within normal reference range) or lower/higher than normal (if value is either below or above the normal reference range).

Applicable laboratory values will also be classified using NCI CTCAE v4.0. Laboratory values within normal range will be categorized as either non-decreasing or non-increasing depending on the direction of the CTCAE grade (decreasing or increasing respectively).

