8.10.3 Clinical Laboratory Evaluations

Laboratory test values at each assessment and for change from baseline to each assessment will be displayed using summary statistics (n, mean, median, and standard deviation).

In addition, shift tables will be presented to display the shift in the normal range categories (L, normal [N], H) from baseline to the final evaluation. Baseline is defined as the latest non-missing value prior to randomization.

Shift table of laboratory assessments with CTCAE grade ≥3 that also worsened from baseline will be presented by visit for each laboratory parameter.

Shift table of baseline to each assessment by CTCAE grade will be summarized. Laboratory tests with CTCAE grades in two directions (increasing and decreasing) will be presented separately for each direction.

All clinical laboratory data will be presented in listings. Within each listing, laboratory values outside the normal ranges will be flagged as either high (H) or low (L).

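### The SAP plans no table of worst post-baseline CTCAE grade for laboratory values, and its nearest-visit rule can leave off-schedule grade ≥3 results in listings only

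*SAP*

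**What the plan says.** **Choice of value.** SAP 6.2.2 sets analysis windows around each scheduled day. If a window contains more than one assessment, "the data from the visit closest to the scheduled study day will be used"; a tie goes to the later visit. Time-to-event analyses instead take the earliest event. There is no separate rule for safety data.

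**Visits summarised.** SAP 6.5.3 states that "scheduled visits for chemistry will include Screening, Week 2, Week 4, Week 8, Week 12, Week 16, Week 20, and Week 24". Hematology and coagulation follow the same list without Week 2. The continuous summaries also include an end-of-study-treatment value.

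**Laboratory tables in SAP 8.10.3:**
- Values and changes from baseline, "displayed using summary statistics (n, mean, median, and standard deviation"), so without minimum or maximum, although SAP 7.1 lists both as standard.
- A normal-range table showing the "shift in the normal range categories (L, normal [N], H) from baseline to the final evaluation".
- A table of severe values: "Shift table of laboratory assessments with CTCAE grade ≥3 that also worsened from baseline will be presented by visit for each laboratory parameter".
- A general grade table: "Shift table of baseline to each assessment by CTCAE grade will be summarized".
- Listings of all laboratory data, with out-of-range values flagged.

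**Adverse events.** SAP 8.10.2 counts the highest CTCAE grade per patient within system organ class or preferred term. The protocol's definition of an adverse event (12.1) covers significant laboratory abnormalities.

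**The concern.** A by-visit laboratory table answers how many patients were at a given grade at Week 8. A safety reader also wants to know how many patients in each arm ever reached grade ≥3 on a given test. No laboratory table in SAP 8.10.3 gives that second figure, although the SAP applies the worst-grade principle to adverse events.

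The window rule adds to this. It chooses by calendar distance, whatever the result. A sample drawn between visits because a patient is unwell is set aside if a routine draw in the same window lies nearer the scheduled day. The protocol expects samples outside the routine visit days. It allows extra clinical management visits between the four-weekly visits (synopsis; 9.1.2.2; 9.1.3.3) and calls for laboratory tests within 7 days before TheraSphere administration (9.1.3.1) and again at re-treatment (9.1.3.2).

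At stake is the description of laboratory toxicity by arm. The protocol's background (5.3) cites a per-patient figure of this kind, grade 3/4 bilirubin toxicity in 19% of a TheraSphere cohort. The planned laboratory tables would yield nothing comparable to it.

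**Working it through.** The documents give no figure on this point, so there is none to reproduce. The check has three steps.

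**1. The rule applied to example days.** Inputs: the windows in SAP Table 3, namely Week 2 (days 1–21), Week 4 (22–42), Week 8 (43–70), Week 12 (71–98) and Week 16 (99–126). The table shows no rows for Weeks 20 and 24, so I assume the 28-day pattern continues: 127–154 and 155–182. In each window the rule keeps the day d with the smallest |d − scheduled day|.

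Take routine draws on days 14, 28, 56, 84, 112, 140 and 168, plus unscheduled draws on days 42 and 48.
- Week 4 window: |42 − 28| = 14 against |28 − 28| = 0, so day 28 is kept.
- Week 8 window: |48 − 56| = 8 against |56 − 56| = 0, so day 56 is kept.

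Both unscheduled values leave any table built on the windows, whatever their grade.

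**2. How readily one unscheduled value is displaced.** Assume one unscheduled draw, equally likely on any of days 1–182, and every routine draw taken.
- Routine draws exactly on the nominal day: the unscheduled value survives only if it falls on one of the 7 nominal days, so the share dropped is 1 − 7/182 = 96%.
- Routine draws varying evenly within the permitted ±7 days: a simulation of 100,000 placements gave 69% dropped.

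These are properties of the rule under the stated placement. They are not rates of missed toxicity, which depend on how often unscheduled samples are taken and what they show.

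**3. What by-visit counts leave open.** Let q be the share of patients at grade ≥3 at each of the 7 post-baseline chemistry visits (Weeks 2, 4, 8, 12, 16, 20, 24), with all patients seen at all visits. The share ever at grade ≥3 is smallest (q) if the same patients are affected each time and largest (7q) if different patients are affected each time. Independence between visits gives 1 − (1 − q)^7. The values of q are assumed.

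| q per visit | Lowest | If independent | Highest |
|---|---|---|---|
| 2% | 2% | 13% | 14% |
| 5% | 5% | 30% | 35% |
| 10% | 10% | 52% | 70% |

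For hematology and coagulation, with 6 visits, the range at q = 5% is 5% to 6 × 5% = 30%. This step does not depend on the window rule: the gap remains even if no value is dropped.

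**The case against.** The strongest reply is that a clinically important laboratory peak already has a worst-grade route. Significant laboratory abnormalities count as adverse events (protocol 12.1), events after treatment start are to be reported (12.5), liver-test changes are listed as expected with TheraSphere (12.6.1), and SAP 8.10.2 tabulates each patient's highest grade. This stands, and it rules out the inference that such values are never tabulated. It does not close the gap. The route depends on the investigator judging the abnormality significant and reporting it, in an open-label trial. SAP 6.5.2 also limits treatment-emergent events to those starting before 30 days after the last dose of sorafenib or TheraSphere.

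Other replies that stand:
- **Wording.** The general CTCAE shift runs to each assessment, which could be read to include unscheduled values. The SAP does not say whether the window rule governs it, and the table shells are a separate document that was not available.
- **Surviving peaks.** An off-schedule peak stays in the by-visit tables if it is the nearest value in its window or the routine draw was not taken.
- **Final value.** A reader might think toxicity grade is also judged on the last value. It is not: the final evaluation feeds only the low/normal/high shift.
- **Data available.** The protocol does not say that laboratory results from extra clinical management visits are entered in the eCRF. A worst-grade table can use only what is recorded.
- **Consequence.** Nothing is lost from the listings, the trial stopped early with few patients, and no inference on adverse events is planned.

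**Conclusion.** The point holds as a reporting gap. SAP 8.10.3 specifies no worst post-baseline laboratory grade per patient, so the planned laboratory tables give no per-patient grade ≥3 rate by arm. If the window rule applies to the CTCAE tables, it can also remove off-schedule grade ≥3 values, which then appear only in listings unless reported as adverse events.

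Only the ambiguity can be sized: under the assumed 5% per visit over seven visits, the share of patients ever affected lies anywhere from 5% to 35%. The number of events hidden in this trial cannot be derived, because the documents give neither the frequency nor the results of unscheduled samples.

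Two stronger readings are not supported:
- A reader might size the loss by dividing the length of an excursion by the 28-day visit interval. That is the chance that a routine draw falls within the excursion. It describes the sampling schedule, not the window rule, and it ignores the Week 2 chemistry draw.
- A reader might treat liver toxicity as the central safety contrast and apply the 19% bilirubin figure to this trial. The documents do not call it that. The cohort was single-centre and included Child-Pugh B patients, whereas this trial enrols Child-Pugh A only, and the protocol does not say that those events were short-lived.

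This is a worthwhile, inexpensive improvement. Efficacy conclusions are unaffected.

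**What to change.** In SAP 8.10.3, add a shift table from baseline to worst post-baseline CTCAE grade per patient, by laboratory parameter, direction (increase or decrease) and arm. Use every recorded scheduled and unscheduled value after the first sorafenib dose or first angiogram.

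In SAP 6.2.2, state that the nearest-to-schedule rule applies only to by-visit summaries. In SAP 8.10.3, state whether the shift to each assessment includes unscheduled values.

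Cost: one further standard table and two sentences of text, with no new data collection and no change to sample size, alpha or power. The consequence to accept is that reported grade ≥3 laboratory rates may be higher than the by-visit tables suggest.

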6.3 Baseline Assessments

Baseline for the following assessments is defined as the last assessment performed on or before the day of randomization.

- Informed Consent
- Inclusion/ Exclusion Criteria
- Demographics (age, gender, race, ethnicity)
- Medical history
- Physical examination
- Vital signs (heart rate [HR], respiration rate [RR], blood pressure [BP], aural temperature, height and weight)
- Disease and treatment history
- ECOG performance status
- Laboratory tests (hematology, coagulation, chemistry)
- Serum pregnancy test
- Child Pugh Score
- Categorization of PVT
- HCC tumor biomarkers- AFP
- Liver volume/mass and tumor burden
- FACT-HEP QOL

- CT/MRI of chest
- CT/MRI of pelvis/abdomen
- Stratification factors: AFP (400 ng/mL or >400 ng/mL) and participating trial site

Time from diagnosis of HCC will be calculated as follows:

Time from diagnosis of HCC (months) to randomization = (Date of Randomization – Date of Diagnosis)/30.4375.

6.4 Efficacy Variables

For all efficacy evaluations, the baseline measurement is defined as the last measurement prior to randomization.

6.4.1 Primary Efficacy Variable – Overall Survival (OS)

The primary study endpoint is OS defined as the time from date of randomization until date of death due to any cause. For each patient that is not known to have died, OS will be censored at the time of last contact date known to be alive (contacts considered in the determination of last contact date include adverse event start and end dates, lesion assessment date, and best available care start and end dates).

Overall Survival (months)= (Date of event/censor – Date of Randomization + 1)/30.4375.

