- Concurrent medication
- Abdomen/pelvic CT scan/MRI (every 8 weeks from randomization)
- Chest CT scan (every 16 weeks from randomization)
- Bone scintigraphy at week 16, every 6 months thereafter

Progression for patient management decision-making: For the purposes of this trial, definition of progression for patient management decisions will include assessment of change in PVT status and tumor progression and is defined as:

- Radiological progression as defined by RECIST v 1.1 (after receiving all allowable TheraSphere treatments as specified by the protocol) And/Or
- Development of extra-hepatic disease beyond the limits defined in the eligibility criteria
- Worsening of PVT from baseline defined as change in classification of PVT (per Shi et al) up to Type IIIa; PVT Type IIIb or Type IV may not be treated
- ECOG Performance Status ≥2

[figure not shown]
Follow up visits following progression: In both arms, after Week 24 or after progression has been confirmed and patients have received all treatments allowed under the protocol, study visits will take place once every 8 weeks until death. These visits can be conducted by telephone at the investigator's discretion, if a PS ≥ 2 (symptomatic progression) is assessed and whenever in the best interest of the patient, and will document:

- ECOG Performance Status (including date of death if applicable)
- Adverse event reporting
- o Concurrent medication (for treatment of HCC only, recording of medications or therapies used in supportive care is not required).

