## 9.1.2.4 Q8 WEEKS FOLLOWING PROGRESSION TO DEATH

Every 8 weeks following determination of progression (Section 9.2.20), until death, a clinic visit or telephone follow-up (at the investigator's discretion, if a PS ≥ 2 (symptomatic progression) is assessed and whenever in the best interest of the patient) will be conducted. The following activities will take place:

- ECOG Performance Status (including date of death, if applicable) will be assessed as described in Section 9.2.6.
- 2. Record any treatment and concurrent medications to treat hepatocellular carcinoma and any adverse events as described in Sections 9.2.18, 9.2.19 and 12.3. Medications and therapies used in supportive care will not be recorded.
- 3. Patient Reported Outcome assessments will be obtained as described in Section 9.2.14 at clinic visits
- Child Pugh status will be assessed as described in Section 9.2.7

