#### 9.1.3.5 Q8 WEEKS FOLLOWING PROGRESSION TO DEATH

Every 8 weeks following determination of progression (Section 9.2.20), until death, a clinic visit or telephone follow-up (at the investigator's discretion, if a PS  $\geq$ 2 (symptomatic progression) is assessed and whenever in the best interest of the patient) will be conducted. The following activities will take place:

- ECOG Performance Status (including date of death, if applicable) will be assessed as described in Section 9.2.6.
- 2. Record any treatment and concurrent medications to treat hepatocellular carcinoma and any adverse events as described in Sections 9.2.18, 9.2.19 and 12.3. Medications and therapies used in supportive care will not be recorded.
- 3. Patient Reported Outcome assessments will be obtained as described in Section 9.2.14 at clinic visits

For patients undergoing retreatment procedures, study visits will occur Q8 weeks, until determination of subsequent hepatic progression, during which the procedures described in Sections 9.1.3.3 and 9.1.3.4 will be completed.

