## 9.2.17 Efficacy Imaging – CT/MRI

Baseline efficacy imaging scans will be obtained during screening and efficacy assessment scans will be taken every 8 weeks post randomization until progression is confirmed (see Section 9.2.20). Most patients will be evaluated by CT images. MRI images are also permitted. The imaging modality used at baseline must continue to be used for all efficacy images throughout the study. Triple phase CT will be used in accordance with site standards at baseline for dosimetry determination. SPECT imaging may be performed according to standard of care practices for clinical management but is not a study requirement.

Spiral CT abdomen/pelvis – must be performed with cuts of 10 mm or less in slice thickness contiguously in the axial plane. From these images, hepatic and extra-hepatic lesions will be read.

Spiral CT Chest – must be performed with cuts of 10 mm or less in slice thickness contiguously in the axial plane. From these images, extra-hepatic lesions will be read.

To enable analysis of secondary study endpoints using radiological assessment, investigators will identify, read and use bidimensional measurements of target lesions for size and will record evidence of enhancement and increase in dimension of a pre-existing thrombus for all image timepoints. These data will be captured on the eCRF. Comparison between baseline and subsequent images of quantitative and qualitative findings will determine response according to RECIST v 1.1, mRECIST and EASL which are assessed separately in secondary endpoint analyses.

Bone Scintigraphy – Bone scintigraphy to assess spread of metastatic disease will be performed according to institutional standards. For patients with AFP > 400 ng/mL at screening, results of bone scintigraphy will be recorded at the screening visit and subsequent study visits according to the site standard practice ( week 16 study visit and 6 months thereafter (i.e. months 10, 16, 22, etc.) ). Bone scintigraphy is suggested whenever there is an unjustified increase in AFP or the patient experiences bone pain or symptomatic deterioration and repeated at a frequency according to site standard practice.

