#### 10.2.2 TRIAL ENDPOINTS

#### 10.2.2.1 PRIMARY EFFICACY ENDPOINT

The primary study endpoint is overall survival (OS) time, which will be calculated as the interval between the randomization date and the date of death for any cause, with censoring at the date of last contact for patients alive at last contact.

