6.4.2.3 Time to Symptomatic Progression

TTSP is defined as the time from date of randomization to date of assessment of ECOG performance status ≥ 2 with or without tumor progression based on investigator assessment. Deterioration in performance status is to be confirmed at one subsequent evaluation 8 weeks later. The first date at which the ECOG performance status was ≥ 2 will be used as the end date in the TTSP analysis (assuming the next subsequent visit confirmed the deterioration).

TTSP (Months) = (Date of ECOG ≥ 2 – Date of Randomization + 1)/30.4375.The censoring is performed as follows:

- If a patient does not have a post baseline ECOG performance status, then the TTSP will be censored at the randomization date;
- 2) If a patient has post baseline ECOG assessment but did not have ECOG ≥2 then TTSP will be censored at the last post baseline ECOG performance status assessment date.

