7.3.1 Partial Date Imputation

Partial dates with day or day and month missing will be imputed as follows:

Missing day only

- The missing day of onset of an AE or start date of a concurrent therapy will conservatively be set as follows:
 - The first day of the AE/concurrent therapy start month, if the month of randomization is before the AE/concurrent therapy start month.,
 - One day after randomization, if the month of randomization is the same as the AE/concurrent therapy start month.
- The missing day of the end date of a concurrent therapy will be set to the last day
 of the month occurrence.
- For other variables, including date of tumor response, progression, death, partial
 dates that need to be imputed will use the 15th of the month to replace the missing
 day. The only exception is when the last visit date is after the 15th of the month
 then death date will use the last visit date on study.

Missing day and month

- If the onset date of an AE or start date of a concurrent therapy is missing both day and month, it will be set as follows:
 - January 1 of the AE/concurrent therapy start year, if the year of randomization is before the AE/concurrent therapy start year,
 - One day after randomization, if the year of randomization is the same as the AE/concurrent therapy start year.

If the resolution date of an AE or end date of a concurrent therapy is missing both day and month, it will be set to December 31 of the AE/concurrent therapy end year.

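### Does the overall-survival censoring rule in SAP 6.4.1 leave out the 8-weekly ECOG contact, or let imputed dates in?

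*SAP*

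**What the plan says.** Protocol 10.2.2.1 measures OS from randomization to death from any cause, "with censoring at the date of last contact for patients alive at last contact". It does not restrict the type of contact. Protocol 10.2.3.2 leaves the detail of censoring to the SAP, and SAP 7.3 points back to Section 6.4.

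SAP 6.4.1 keeps the protocol's rule and adds the note: "contacts considered in the determination of last contact date include adverse event start and end dates, lesion assessment date, and best available care". SAP 6.5.1.3 uses the same known-alive date for duration of survival follow-up, without any list.

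After progression the synopsis says that "study visits will take place once every 8 weeks until death", in person or by telephone. At that contact, "ECOG Performance Status (including date of death, if applicable) will be assessed as described in Section 9.2.6" (Protocol 9.1.2.4; 9.1.3.5 is the same for the TheraSphere arm). Adverse events (AEs) and treatment for HCC are recorded at the same contact.

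Routine scans end earlier: "efficacy assessment scans will be taken every 8 weeks post randomization until progression is confirmed" (Protocol 9.2.17). The exception is in 9.1.3.5: "For patients undergoing retreatment procedures, study visits will occur Q8 weeks, until determination of subsequent hepatic progression".

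On imputation, SAP 7.3.1 takes an AE or therapy end date with day and month missing, and "it will be set to December 31 of the AE/concurrent therapy end year". SAP 8.8 applies 7.3.1 to the post-progression care pages.

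**The concern.** The one contact scheduled to establish whether a progressed patient is alive is not among the sources named for OS censoring. Once scans stop, the named sources give a date only if an AE or HCC treatment is recorded. An uneventful telephone call to a living patient gives none. If the note were programmed as a closed list, such a patient would be censored before the last date known alive. Deaths keep their full time and only survivors lose time, so the Kaplan-Meier medians fall. The hazard ratio could move either way, because time to progression, re-treatment scanning and date capture may differ by arm.

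There would be a visible oddity too. For a patient who never reaches ECOG 2, SAP 6.4.2.3 says "then TTSP will be censored at the last post baseline ECOG performance status assessment date", so time to symptomatic progression could run past OS.

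The second worry points the other way. An end date imputed to 31 December could fall after the patient was last known alive, and 6.4.1 does not expressly exclude it. The trial stopped early (SAP 5), which can leave more survivors censored, and the reverse Kaplan-Meier follow-up in SAP 8.10.1.3 uses the same dates.

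**Working it through.** **1. Rule against note.** The operative words in SAP 6.4.1 are the rule: the latest contact with a patient known to be living. The note opens with *include*, which marks examples. The wider reading agrees with Protocol 10.2.2.1 and with the unlisted wording in SAP 6.5.1.3. The closed-list reading agrees with neither.

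**2. Does an ECOG contact qualify?** Performance status, or a date of death, is recorded at it. A performance status recorded for a living patient shows the patient alive on that date.

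**3. Would a closed list be noticed?** SAP 6.4.1 computes OS as (event or censoring date − randomization + 1)/30.4375. SAP 6.5.1.3 computes survival follow-up as (death or last-known-alive date − randomization + 1)/30.4375. The two should be equal in every patient. If OS used the closed list and follow-up the full known-alive date, they would differ.

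**4. Imputed dates.** With true end dates spread evenly over a 366-day year, moving them to 31 December overshoots by 182.5 days on average (182.5/30.4375 = 6.0 months) and by 365 at most (12.0 months). Month-end imputation overshoots by at most 30 days (0.99 month). These are errors in an AE or therapy end date. They reach OS only if the patient is a survivor, the date is partial, no later contact exists, and the filled-in date is taken as proof of life. Section 7.3.1 does not mention last contact, and 8.8 uses it for medication reporting.

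**5. Size if the list were closed.** No figure in the plan depends on this point, so there is none to reproduce. All inputs below are assumptions: exponential OS with medians 9 v 13 months (the design values) or 9 v 9; median time to progression 5.5 in both arms, or 5.5 v 7.9 (values quoted in Protocol 5.3); correlation between the two 0 or 0.6; 0% or 30% of TheraSphere patients scanned on after re-treatment; 8-weekly visits; 200,000 patients per arm. *Capture* is the chance that a post-progression visit yields a listed date. The 75% and 90% rows were run for 9 v 13 only.

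| Accrual + follow-up (months) | Capture | Medians, control/TheraSphere | Change in HR |
|---|---|---|---|
| 42 + 12 (planned) | 25–50% | lower by at most about 0.3 | at most 0.013 |
| 42 + 12 | 75–90% | not tabulated | at most 0.001 |
| 24 + 3 (assumed) | 25% | 8.7/12.5 become 8.2–8.5/11.4–12.1 | −0.035 to +0.015 |
| 24 + 3 | 50% | become 8.5–8.6/12.0–12.3 | −0.014 to +0.005 |
| 24 + 3 | 75% | lower by roughly 0.1 | at most 0.003 |
| 24 + 3 | 90% | lower by about 0.03 | at most 0.001 |

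With capture of 50% in one arm and 25% in the other, a true HR of 1 would read 0.98–1.03 (42 + 12) or 0.94–1.06 (24 + 3).

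**6. Cruder stress test.** Exponential OS with medians 9 and 13, 2,000 runs per setting.

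- Every survivor censored 0–6 months too early, 320 patients, 42 + 12: HR 0.693 becomes 0.695, or 0.721 if only the TheraSphere arm is affected.
- The same with an assumed 60 patients, 30 months' accrual and no further follow-up: medians 9.0/13.1 become 8.2/11.6, and HR 0.679 becomes 0.686, or 0.784 if only the TheraSphere arm is affected.
- 20% of survivors dated 0–12 months too late: with 320 patients HR stays 0.693 (0.684 if TheraSphere only); with 60 it is 0.680 (0.643 if TheraSphere only).

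**7. Scale.** With 1:1 allocation SE(log HR) ≈ 2/√deaths. At the planned 250 deaths it is 2/√250 = 0.126; a shift of 0.013 on an HR of 0.69 is 0.013/0.69 = 0.019 on the log scale, about 0.15 of that SE. With 60 patients SE is at least 2/√60 = 0.258; the worst case above is ln(0.784/0.679) = 0.144, a little over half of it.

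**The case for a change.** The best argument for a change is that this is the primary endpoint of an open-label, early-terminated trial, and that fixing the censoring date is the SAP's job. Two programmers could derive different dates from the same sentence. Section 7.3.1 already uses the last visit date when it completes a partial death date, so its absence from the note in 6.4.1 looks like an oversight. One sentence would settle it, with no new data. In a small trial with many survivors, a lag in one arm alone takes the HR from 0.679 to 0.784.

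Part of this stands. The contact is not named, imputed dates are not expressly barred, and a clarifying sentence would do no harm if drafted with care. It should not, for example, count an administrative study-exit date as contact with a living patient.

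The rest does not carry. The rule itself gives the right date, and the 7.3.1 provision shows that visit dates are already used in the survival derivations. The 0.784 needs a closed list, a lag of up to six months for survivors in the TheraSphere arm only, and an assumed trial size and cut-off. The documents support none of these. Because AEs and HCC treatment are recorded at the same visits, and AEs until study exit (Protocol 12.3), many visits would give a listed date even under the closed reading.

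**Conclusion.** No change is called for. SAP 6.4.1 states a censoring rule that agrees with the protocol and illustrates it with an open list. An analyst applying the rule would count the ECOG clinic or telephone contact and would not treat an imputed 31 December as proof of life. What is missing is detail of the kind a programming specification fills.

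If the list were nevertheless programmed as closed, the effect at the planned follow-up would be negligible: at most about 0.3 month on the medians and 0.013 on the HR at 25% to 50% capture, and less at higher capture. Under an assumed early cut-off of 24 + 3 months the HR changes by −0.035 to +0.015 at 25% capture and by at most 0.003 at 75%. All of these rest on assumed capture rates, progression times and cut-offs. The documents do not give the number of survivors, the capture rate or the cut-off date, so the real size cannot be derived. The late-censoring effect has no documented basis for sizing either, and needs a rare combination of partial dates and missing later contacts.
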